4.1.2. Exclusion criteria in pregnant volunteers

- Pregnancies with:
  - Major fetal abnormalities in the current pregnancy such as: lethal malformations, or requiring pre- or post-natal surgery; and fetal death prior to randomization.
  - History of rupture of membranes or prophylactic cerclage in the current pregnancy before inclusion into the study.
    - Cervical and/or vaginal injuries prior to insertion of the pessary (e.g., cervical erosion secondary to trauma, infection or carcinoma, vesicovaginal or rectovaginal fistulas).
    - Unconscious, severely ill, mentally disabled patients, or under 16 years of age.
    - Patients for whom use of progesterone is contraindicated.
    - Participants with history of thrombosis.

## 5 PROCEDURES

### 5.1. Recruitment and Screening

Patients will participate voluntarily and under informed consent. Participant selection will be performed by screening the general population of pregnant women with single fetus monitored by the Hospital Healthcare Network, to investigate by serial transvaginal ultrasound performed between gestation weeks 16 (0/7) and 24 (0/7) those patients who have a cervical length between 10 mm and 25 mm, and/or women with a single fetus and cervical length  $\geq 10$  mm presenting one or more of the following risk factors: a) preterm birth prior to 35 (34 6/7) weeks of gestation; b) premature rupture of membranes prior to 35 (34 6/7) weeks of gestation.

Gestational age will be determined by the last menstruation date and will be confirmed by measurement of the craniocaudal length obtained in the first trimester ultrasound, or by measurement of the cephalic circumference in the second trimester ultrasound predominating the actual date of the last menstrual period (LMPad).

The selected volunteers will be examined and those with vaginal discharge will undergo clinical examination and/or bacteriological investigation and if confirmed for infection, this will be treated with the appropriate antibiotic. In these cases, insertion of the sustained-release progesterone cerclage pessary will be performed subsequent to the end of treatment although before 24 (0/1) weeks of gestation.

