#### 5.4. Intervention and follow-up

The intervention and follow-up of participants will begin after the conditions eligible to participate in the study are verified, proceeding as follows:

5.4.1. For selected participants with pre-existing risk factors, these are: immediately previous pregnancy terminated prematurely with preterm birth, or premature rupture of membranes before 35 weeks of gestation; placement of a progesterone cerclage pessary, or treatment with progesterone capsules will start at week 16 (0/7) but not beyond 24 (0/7) weeks of gestation. These participants will have a transvaginal ultrasound performed to document the length ( $\geq 10$  mm) and position of the cervix at the placement of the pessary or the start of treatment with vaginal progesterone capsules.

5.4.2. For pregnant patients with a single fetus, selected for the presence of a shortened cervix (between 10 mm and 25 mm), the pessary will be inserted or the vaginal administration of progesterone capsules will be started at the time of the investigation, but not before 16 (0/7) weeks of gestation and not after 24 (0/7) weeks of gestation. The cervix angulation relative to the uterus body using the intersection of the uterus posterior wall longitudinal axis with the cervical canal axis in addition to a measurement of the cervical length will be performed on 60% of the study participants assigned to one of the two groups with medicated pessary, prior to insertion of the pessary and after its insertion, by means of a transvaginal ultrasound technique recently described (25). The transvaginal ultrasonography post-insertion of the pessaries may be performed at visit one or at visit two at the latest.

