#### 5.5. Placement and repositioning of the cerclage pessary containing sustained-release progesterone

Once the cervix length and positioning have been examined by transvaginal ultrasound, and any vaginal infection has been ruled out or treated, the progesterone pessary should be implanted by a professional qualified and trained for that purpose. For placement, the participant must be lying in supine position.

The removal of the pessary will be done by vaginal examination at week 36 6/7 or earlier, if there is any medical indication for induction of premature labor or elective cesarean section. The pessary will also be removed from participants in preterm birth labor not responding to treatment with tocolytics.

During controls or visits to emergency departments or medical offices, participants who report vaginal discharge should be examined by a physician to rule out infection by relevant testing (vaginal discharge smears for PCR), and deliver the appropriate treatment without the need to remove the pessary. This condition will be considered an adverse event.

In the event that the medicated cerclage pessary is spontaneously expelled it, will be repositioned within maximum 72 hours; if this does not occur, the patient will be withdrawn from the study but considered in the final statistical analysis under the intention-to-treat principle.

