5. ANALYSIS CONVENTIONS

The statistical analysis will be made by ILS Clinical Research under the authorization of Laboratorio Andromaco S.A.

GENERAL PRINCIPLES

The statistical analysis will be provided to give a general summary of the study subjects and a vision of the efficacy and safety of the results. The data provided by the sites will be summarized for this purpose. Tables of absolute and relative frequencies will be constructed for the quality variables. All the percentages will be presented with a decimal. The quantitative variables will be summarized with the number of subjects participating (n), mean, standard deviation (SD), and median, maximal and minimal.

Two tailed test will be carried out for all the analysis and the type I error is 0.05 for continuous variables and the discrete variables. All p values shall be rounded to three decimal and the values under 0.001 will be presented as <0.001 and values greater than 0.999 will be presented as 1.000. A comparison of the treatment groups will be done with respect to the demographic and baseline characteristics using inferential statistical techniques to detect if any of these variables may condition the results in the dependent variables. Comparisons in qualitative variables will be carried out using the Cochran-Mantel-Haenszel (CMH) test of general association, while the comparisons in quantitative variables will be made with a test of comparison of means (ANOVA analysis of variance) for independent samples with normal distribution. In the cases of no normality on the continuous variables, or in case of not belonging to the exponential family for discrete data, the parametric tests will be replaced for nonparametric tests such as Kruskal-Wallis or Friedman. These tests will be presented in each table as deemed necessary. All confidence intervals will be two-tailed and at 95%.

Table 1: Study Schedule of Assessments

Activities	Visit 1	Visit 2	Visit 3	Visit 4	Visit 5	Visit 6	Visit 7	Final Visit
Demography	X							
Medical History	X							
Physical Exam	X	X	X	X	X	X	X	X
Gynecological Exam	X							
Vital Signs	X	X ¹	X ¹	X ¹	X ¹	X ¹	X ¹	X ¹
Transvaginal Ultrasound	X	X ²	X	X	X	X	X	X
Pre-birth Control	X							
Obstetric Background	X							
Lab Tests (Blood and Urine)	X							
Eligibility	X							
Vaginal Discharge	X	X ³	X ³	X ³	X ³	X ³	X ³	X ³
Randomization	X							
Pessary Insertion	X							
Acceptability and tolerance to the insertion	X							X
Concomitant Medications	X	X	X	X	X	X	X	X

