6. POPULATION DEFINITIONS

In order to meet the needs of the sub-groups of the Protocol, the following population sub-groups are defined:

Per Protocol (PP): It is defined as the subset of participants who meet the criteria of selection, who expressed their desire to participate in the study, who signed the informed consent form, that the drug has been administered to them and have completed all the visits required or till the termination of the pregnancy as per Protocol.

Intention to treat (ITT): It is defined as the subset of participants who meet the selection criteria, showing their desire to participate in the study, who signed the informed consent form, that the drug has been administered to them, who have at least completed the initial visit and at least one of the subsequent visits to the pessary referred to in the Protocol.

The main efficacy analysis will be carried out with a focus Per Protocol (PP), however it will also be carried out per Intention to Treat (ITT) all the analysis. Otherwise, the main safety analysis will be completed as ITT.

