- (iv) Expulsion of the Pessary (Yes/No, Final Visit). The date, gestational age of expulsion of the pessary without replacement will be recorded in the log.
- (v) Sensation upon the release of the pessary (Final visit). This question has the following categories: 1 = never, 2 = almost never, 3 = occasionally, 4 = frequently, 5 = always; and only one of them will be selected.
- (vi) Release of vaginal fluid (Final visit). This question has the following categories: 1 = never occurred, 2 = No changes, 3 = little increase, 4 = big increased 5 = change in color; and only one of them will be selected.
- (vii) Sexual intercourse with pessary (Final Visit). This question has the following categories: 1 = better, 2 = as always, 3 = with discomfort, 4 = with pain, 5 = no intercourse; and only one of them will be selected.
- (viii) Request for early withdrawal of the pessary (Yes/No, Final visit). The date, gestational age and reason of withdrawal from the pessary will be recorded in the log.
- (ix) Recommendation (Yes/No, Final Visit).

For all the above items except number (iii), the information will be summarized in the frequency and percentage tables according to the total number of subjects included in each treatment group and will be handled only for informatory purposes.

Changes in vaginal discharge

Clinical evaluation and/or bacteriological research will take place, infections will be treated with the appropriate antibiotic in case it is confirmed. For these cases, the insertion of a cerclage pessary with sustained-release of progesterone, will take place later at the end of the treatment, but before 24 (0/1) weeks of gestation. It will be monitored in each visit.

In each control, the participant will be asked about the presence, quantity and physical characteristics of the vaginal discharge. To discard presence or absence of infections, the subject will be asked about the need to do a smear of the vaginal discharge for PCR and the need for treatment. The information will be summarized in tables of frequencies and percentages based on the total number of subjects included in each treatment group per visit. A generalized CMH test will be used to assess whether changes in vaginal discharge were different in any of the groups through time.

Children Evaluation

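### A woman randomised to a pessary but never fitted because of an entry infection falls outside both SAP analysis sets, and the documents do not fix the order of infection treatment, randomisation and treatment start

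*Protocol*

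**What the plan says.** **Infection at entry.** Protocol 5.1 sets the step out under recruitment and screening: "The selected volunteers will be examined and those with vaginal discharge will undergo clinical examination and/or bacteriological investigation". If infection is confirmed it is treated, and then "insertion of the sustained-release progesterone cerclage pessary will be performed subsequent to the end of treatment although before 24 (0/1) weeks of gestation". Protocol 5.5 repeats the condition for placement: "any vaginal infection has been ruled out or treated, the progesterone pessary should be implanted by a professional qualified and trained". SAP section 10, under changes in vaginal discharge, says that insertion in these cases "will take place later at the end of the treatment, but before 24 (0/1) weeks of gestation". None of these places mentions the capsules, and protocol 5.6, on capsule adherence, has no counterpart.

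**Start of treatment.** For women selected for a short cervix, protocol 5.4.2 says that "the pessary will be inserted or the vaginal administration of progesterone capsules will be started at the time of the investigation", between 16 (0/7) and 24 (0/7) weeks. Protocol 5.4.1 gives women selected on history the same window.

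**Schedule.** SAP Table 1 marks the vaginal discharge check, eligibility, randomisation and "Pessary Insertion" at Visit 1. It gives no order within the visit, and insertion appears at no later visit.

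**Analysis sets.** In SAP section 6 the ITT set is limited to women "that the drug has been administered to them, who have at least completed the initial visit and at least one of the subsequent visits". The PP set also requires that the drug was administered, plus all required visits or visits until the pregnancy ended. PP is the main efficacy set; ITT is run as well. SAP section 5 leaves women with baseline data only out of tables and figures. For the pessary arms, SAP section 9 records only removal.

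**Protocol principle.** Protocol 5.5 and 5.7 invoke intention to treat for expulsion and removal, and 5.6 keeps poorly adherent capsule users in the analysis. A pessary that was never inserted is not addressed. SAP section 1 makes the protocol the final reference.

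**The concern.** Taken together, these passages allow an exclusion after randomisation that depends on the assigned arm. Suppose a woman is randomised at Visit 1, is found to have an infection and is assigned a pessary. She waits for antibiotic treatment to end. If she passes the gestational limit or delivers before insertion, she has received no study drug and leaves both sets. The infection rule creates no such wait for a woman on capsules.

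The women lost this way are selected for genital infection. If infection raises the risk of early spontaneous birth, removing them lowers the observed event rate in the pessary arms without any treatment effect. Women who wait and are then fitted carry untreated time in the pessary arms, which acts in the opposite direction. The two effects need not cancel, and under the SAP as written neither would show in the tables: non-insertion is not captured as a compliance outcome, and no summary of time to first dose is planned.

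**Working it through.** **1. Who leaves which set under SAP section 6**

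| Woman assigned a pessary | PP | SAP ITT |
|---|---|---|
| Fitted late, later visits completed or followed to end of pregnancy | in | in, after one later visit |
| Fitted late, no later visit | depends on the required visits or end of pregnancy | out |
| Never fitted | out | out |

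Only the last row is produced directly by the infection rule. The drug-administered condition applies to every arm, so it would also remove a capsule woman who never started, but the infection rule does not create that case.

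**2. Inputs**
- From the documents: 99 women enrolled per arm (protocol 9.1; 90 × 1.10 = 99), and an entry window of 16 to 24 weeks, which is 8 weeks or 56 days.
- Assumed, because the documents are silent: share infected at entry q = 10–30%; treatment time d = 7–10 days; entry uniform over the window; randomisation before treatment of the infection; overall event rate p = 20%; risk ratio of the event in infected women k = 2, with 3 as a sensitivity value.

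**3. Number delayed and number never fitted, per pessary arm**
- Delayed = 99 × q = 9.9 to 29.7.
- A woman entering in the last d days of the window cannot be fitted in time, so the share never fitted is d/56 = 7/56 to 10/56 = 12.5% to 17.9%.
- Never fitted = 99 × q × d/56. Lower end: 9.9 × 7/56 = 1.2. Upper end: 29.7 × 10/56 = 5.3.
- At least 82% of the delayed women are therefore fitted late and can stay in the sets. Deliveries during the wait are not counted here and would add to the exclusions.

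**4. Shift in the event rate with no true treatment effect**

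The rate in uninfected women is r = p / (1 + q(k − 1)), and in infected women kr. Events before exclusion are 99 × 0.20 = 19.8.
- Lower end (q = 10%, d = 7, k = 2): r = 0.20/1.1 = 0.182, kr = 0.364. Events removed = 1.24 × 0.364 = 0.45. Rate = (19.8 − 0.45)/(99 − 1.24) = 19.8%.
- Upper end (q = 30%, d = 10, k = 2): r = 0.20/1.3 = 0.154, kr = 0.308. Events removed = 5.30 × 0.308 = 1.63. Rate = (19.8 − 1.63)/(99 − 5.30) = 19.4%.
- Upper end with k = 3: r = 0.20/1.6 = 0.125, kr = 0.375. Events removed = 1.99. Rate = (19.8 − 1.99)/93.70 = 19.0%.
- With k = 1 there is no shift, only a loss of numbers.

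**5. Stress test, with the share never fitted set freely (p = 20%)**

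| Infected | Never fitted, of those | k | Excluded of 99 | Pessary rate | Two-sided type I error |
|---|---|---|---|---|---|
| 10% | 50% | 2 | 5.0 | 19.1% | 0.052 |
| 10% | 100% | 2 | 9.9 | 18.2% | 0.061 |
| 20% | 100% | 3 | 19.8 | 14.3% | 0.165 |

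The error rate is clearly inflated only when infection is common, insertion never follows and infection strongly raises risk.

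**6. Same calculation with all randomised women analysed as assigned**

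Nobody is removed for non-insertion, so the difference produced by this exclusion is zero.

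**The case against.** The strongest reply is that the documents do not say that randomisation comes before the infection is treated. The rule sits under screening, concerns selected volunteers, and precedes the sections on groups and randomisation. Protocol 5.4 starts the intervention only once eligibility is verified. Since Table 1 ties randomisation and insertion to one visit, a deferred insertion could mean a deferred randomisation too. This stands as a possible reading. But no passage states it, and Table 1 read plainly puts randomisation at the visit where the infection is first looked for. Different sites could apply different orders.

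A reader might also infer that infected women on capsules start at once. That rests on silence: the timing sentence in 5.4.2 covers both modalities in the same words and only the short-cervix group. What is documented is that the deferral names the pessary alone.

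A reader might infer, further, that every delayed pessary woman drops out of both sets. SAP section 6 does not support that, as step 1 shows.

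Finally, the drug-administered condition is the root of the exclusion and applies to all arms. That is correct, and it is why the main remedy belongs in SAP section 6. The infection rule adds a route into that condition that exists only for the pessary and is tied to a possible risk factor.

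**Conclusion.** The concern holds in a limited form. A randomised woman who is never fitted is in neither SAP set, and the protocol's intention-to-treat statements do not reach her case. If randomisation precedes infection treatment, the infection rule produces such women in the pessary arms only. Under the stated assumptions they number about 1 to 5 per arm of 99, and an assumed 20% event rate moves to between 19.8% and 19.0%. The exclusion would favour the pessary if infection raises risk; untreated waiting would work against it, and the net direction cannot be derived from the documents. The bias is likely small. The reason to act is that the exclusion is arm-related, avoidable and nearly free to remove. The documents do not support the stronger conclusion that infected pessary women are generally lost from the analysis, or that an immediate capsule start is an established difference between the arms.

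**What to change.** **Analysis.** In SAP section 6, define the ITT efficacy set as all randomised women, analysed in the assigned arm from randomisation, including those never fitted or never started. This follows the protocol's intention-to-treat principle. Because PP is named the main efficacy set, redefining ITT alone leaves the exclusion in the main analysis, so the primary comparison should be read from the all-randomised set with PP beside it. Report by arm the number never treated, with the reason, and the days from randomisation to first dose.

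**Reconciliation.** Protocol 5.1, 5.4 and 5.5, SAP Table 1 and SAP section 10 must be reconciled on the order of infection check, randomisation and treatment start, and on what applies to the capsule arm while an infection is treated. That clinical choice is the sponsor's. Protocol 5.3 and Table 1 should then state the order so that all four sites follow it.

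**Cost.** Some wording, one extra summary table and a small amount of analysis. Birth outcomes of untreated women can come from hospital records, which protocol 5.8 already names as a source. Including women never treated dilutes any true effect slightly. The analysis change alters no care and can be made even if enrolment has finished.

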### 5.2. Study groups

Patients will be randomly assigned to the following 3 study groups:

- Control study group: They will be instructed to administer a micronized progesterone 200 mg capsule by vaginal route on a daily basis.
- Pessary study group A: They will have a pessary with 6.3 g of sustained-release progesterone inserted for a period of about 4 to 5 months. This procedure will be performed by a professional qualified and trained for these purposes.
- Pessary study group B: They will have a pessary with 7.7 g of sustained-release progesterone inserted for a period of about 4 to 5 months. This procedure will be performed by a professional qualified and trained for these purposes.

### 5.3. Randomization

The randomization program will be generated by an independent statistician. This program will be linked in sequential numbers with the treatment code randomly assigned. The randomization plan will be kept by a qualified person from Laboratorio Andromaco until the database is clean and ready for analysis. Treatment will be dispensed according to the randomization plan. Women with single pregnancy chosen will be randomized to receive one of the vaginal formulations of the study. For the next volunteer, the Site will have the next randomized number available. Each woman will receive only the formulation corresponding to their randomization number. The investigator will record on the file the randomization number and the code printed on every formulation container. The coordinator of each site will assign the randomization code to the volunteers.

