## 4 STUDY DESIGN

The study will be conducted in compliance with the protocol, the good clinical practice standards, and the provisions of the corresponding ethics committee.

This will be a randomized, open-label, controlled, multicenter, exploratory Phase II study of efficacy. Pregnant patients with a single fetus who after reading the informed consent voluntarily agree to participate in the study will be included.

For secondary outcomes, patients will be their own controls on the following endpoints to be tested: cervix anatomical features—position and length—; plasma and endometrial progesterone concentrations in non-pregnant menopausal women; surveys on pregnant women to establish the acceptability and tolerance of the intervention; and local and systemic safety issues.

4.1. Pregnant Volunteers: 270 + 10% pregnant women at risk of preterm birth from the 4 participating sites will be recruited. This population will be divided into 3 treatment groups with 90 participants each.

They will be informed and invited to participate in the study at prenatal and/or ultrasound control between 16 and 24 weeks of gestation. Volunteers will be included in all cases up to 24 (0/0) weeks of gestation. Volunteers will be selected on the basis of their clinical history and by transvaginal ultrasound performed between weeks 16 and 24. All volunteers with a single pregnancy and cervical length  $\leq 25$  mm but  $\geq 10$  mm will be invited to participate in the study. Prior to inclusion in the study, fetal vitality or other exclusion factors discussed in detail below will be confirmed. Those patients who do not agree to participate in the study will receive the current standard care at each participating site depending on their condition.

4.1.1. Inclusion criteria in pregnant volunteers:

- Pregnant women with a single fetus with a cervical length of 10-25 mm between 16 and 24 weeks of gestation with no pre-existing risk factors.
- Women with ongoing pregnancy between 16 and 24 weeks of gestation with a single fetus and cervical length  $\geq 10$  mm, and having pre-existing risk factors in the immediately previous pregnancy characterized by:
  - Preterm birth before week 35 (with a viable fetus).
  - Premature rupture of membranes before week 35 (with a viable fetus).

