## 6 MATERIALS AND SUPPLIES

Cerclage pessaries containing sustained-release progesterone will be manufactured by Laboratorios Andrómico S.A. Both the pessaries as well as the 200 mg progesterone soft capsules to be administered by vaginal route will be supplied to participants free of charge by Laboratorios Andrómico S.A.

- Vaginal formulations of the study:
  - Capsules containing 200 mg of micronized progesterone for vaginal administration.
  - Vaginal device consisting of a cerclage pessary containing 6.3 g of sustained-release progesterone.
  - Vaginal device consisting of a cerclage pessary containing 7.7 g of sustained-release progesterone.

Laboratorios Andrómico S.A. will be responsible for printing the applicable codes on every container of study formulation.

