The sample size calculation is based on the power to detect differences in the proportion of spontaneous birth between 32 and 34 weeks of gestation, between the formulations of cerclage pessaries with respect to the control group (vaginal progesterone 200 mg capsules). Data collected of at least 90 women in each group will provide at least 80% of the power to detect differences with a rate of 40% or more, using a test of Chi-square of two tails with $\alpha = 0.05$ without correction.

We estimate that up to 10% of the enrolled women may not complete the study, so it must be planned to enroll at least 99 pregnant women in each group to reach at least 198 treated subjects with cerclage pessary and 99 subjects treated with soft capsules of progesterone as a control group (i.e. 99 per each vaginal formulation).

RANDOMIZATION

The randomization will be generated by an independent statistician. The program will be linked in sequential numbers with the code of randomized treatment. A qualified staff member of ANDROMACO laboratory will keep randomization codification, until the database is clean and ready for analysis. The treatment will be dispensed according to the randomization code, the women with unique pregnancy enrolled, will be randomized to receive one of the vaginal formulations of the study.

For the next volunteer, the site will have the next randomization number available. Each woman will receive only the formulation corresponding to the randomization number. The Investigator will record on the log the randomization number and the printed code on each formulation container. Each sites coordinator will assign the randomization code to the volunteers.

Subjects will be randomized to the following three study groups:

- Control Group (A): Intravaginal capsule of micronized progesterone 200 mg on a daily basis.
- Pessary Group (B): Pessary with 6.3 g of sustained release progesterone for a period of around 4 to 5 months.
- Pessary Group (C): Pessary with 7.7 g of sustained release progesterone for a period of around 4 to 5 months.

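### Neither the protocol nor the SAP hides the next allocation from the site until a woman is irrevocably enrolled, so foreknowledge of pessary versus capsule cannot be ruled out

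*Protocol*

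**What the plan says.** Protocol section 5.3 describes the allocation chain:

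- Generation: "The randomization program will be generated by an independent statistician".
- Custody of the list: "The randomization plan will be kept by a qualified person from Laboratorio Andromaco until the database is clean and ready for analysis".
- At the site: "For the next volunteer, the Site will have the next randomized number available".
- Assignment: "The coordinator of each site will assign the randomization code to the volunteers".
- Recording: "The investigator will record on the file the randomization number and the code printed on every formulation container".

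Protocol section 6 adds that the sponsor "will be responsible for printing the applicable codes on every container of study formulation", and lists three products: 200 mg capsules and a pessary device in two strengths. Protocol section 4 sets the design: "This will be a randomized, open-label, controlled, multicenter, exploratory Phase II study of efficacy".

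SAP section 3 restates the procedure ("For the next volunteer, the site will have the next randomization number available") and adds nothing on concealment, block size or stratification. SAP Table 1 places the ultrasound, eligibility, randomisation and pessary insertion all at Visit 1.

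**The concern.** Randomisation protects a comparison only if whoever decides whether, and when, to enrol a woman cannot know which arm she would receive. Here the next number is held at the site, a member of site staff assigns it, treatment is open-label, and a pessary cannot be confused with a supply of capsules once either is seen. Nothing in the text stands between the site and the identity of the next treatment.

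At stake are the two comparisons with control, 6.3 g versus capsules and 7.7 g versus capsules. If women with a shorter cervix or a worse history were approached, or delayed, according to a known next arm, the arms would differ in baseline risk and the difference could be read as a treatment effect. The protocol's Rationale itself says that risk rises as the cervix shortens, and women admitted on history have no upper limit on cervical length. Baseline risk among eligible women can therefore vary widely.

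**Working it through.** The documents give no figure for this point, so the main check sets the text against what concealment needs.

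| Needed for concealment | What the documents give |
|---|---|
| Sequence made by someone outside the site | Yes: independent statistician (Protocol 5.3) |
| Full list kept away from the site | Yes: sponsor employee (Protocol 5.3) |
| Next treatment unknown to the site until enrolment is final | Not stated; the next number is at the site and the coordinator assigns it |
| Packaging that hides the product | Not stated; only a printed code (Protocol 5.3 and 6) |
| Number released only after consent, eligibility and baseline scan are recorded | Not stated; Protocol 5.4 puts eligibility before treatment, and SAP Table 1 lists both eligibility and randomisation at Visit 1 without a lock |
| Blocking, if any, unknown to sites | Not stated |

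The first two safeguards are present and the other four are missing.

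**Does the analysis repair it?** No. SAP section 10 compares proportions by a CMH test with no strata named and no baseline adjustment of the primary comparison. SAP section 6 makes the per-protocol set primary, and its ITT set requires treatment given and at least one later visit. A woman assigned but never treated falls out of both sets.

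**Illustration of scale (assumed inputs).** Suppose half of all women are higher risk, and steering makes that share 60% in one arm and 40% in the other. With risks *h* (higher) and *l* (lower) and no treatment effect, the arm rates are

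p1 = 0.6h + 0.4l and p2 = 0.4h + 0.6l.

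With n = 90 per group (Protocol 9.1), d = p1 − p2 and p̄ = (p1 + p2)/2:

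- SE0 = √[2p̄(1 − p̄)/n]
- SE1 = √[(p1(1 − p1) + p2(1 − p2))/n]
- Rejection rate = 1 − Φ[(1.96·SE0 − d)/SE1] + Φ[(−1.96·SE0 − d)/SE1]

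| h | l | p1 | p2 | Rejection rate (nominal 5%) |
|---|---|---|---|---|
| 20% | 5% | 14% | 11% | 9.3% |
| 30% | 5% | 20% | 15% | 14.2% |
| 40% | 10% | 28% | 22% | 15.3% |

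For the last row, SE0 = √(2 × 0.25 × 0.75/90) = 0.0645 and SE1 = √[(0.2016 + 0.1716)/90] = 0.0644. The upper tail is 1 − Φ[(0.1265 − 0.06)/0.0644] = 0.151 and the lower tail about 0.002, together 0.153.

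**Why blocking matters.** No blocking is stated. Suppose blocks of 3 within site, known to staff, with one capsule and two pessary places. Past assignments are known because treatment is open and the pregnancy card shows pessary or capsule (Protocol 5.4.5). The first woman's product is never certain. The second's is certain if the first received capsules (probability 1/3). The third's is always certain. The share of women whose product is certain in advance is (0 + 1/3 + 1)/3 = 4/9, or 44%.

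**The case against.** The strongest reply is that this is silence, not a shown defect, and several parts of it are fair.

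- **The site holds a number, not the list.** The investigator records both a randomisation number and a container code, which fits kit codes that are independent of the sequence. Dispensing according to the plan also fits release by the sponsor's list holder. Both readings are possible; the text settles on neither.
- **The coordinator assigns, but is not said to recruit.** This is correct. Equally, no text separates the two roles.
- **Timing discretion is limited.** Protocol 5.4.2 has women with a short cervix start when they are examined. That narrows the scope for waiting in that group. Women entered on history may start at any time from 16 0/7 to 24 0/7 weeks, and discretion over whom to approach remains for all. The delay for infection concerns pessary insertion, and the text does not say that randomisation is postponed.
- **There is ordering text.** Consent precedes procedures (Protocol 11), exclusions are checked before inclusion (Protocol 4.1), and eligibility precedes treatment (Protocol 5.4). None of these prevents knowledge of the next arm before a woman is approached.
- **The SAP compares baseline characteristics by arm.** That could reveal gross steering on recorded factors. It does not prevent steering or correct for it.

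Three stronger readings are tempting but unsupported. A reader might infer that staff can see the sequence, or that the product behind the next number is on the shelf; packaging and stock arrangements are not described. A reader might extend the concern to 6.3 g versus 7.7 g; nothing shows that the two pessaries look different. A reader might size the bias from the 70% and 40% figures in the Rationale; those are for birth before 35 weeks by gestational age at detection, so neither the endpoint nor the risk factor matches.

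**Conclusion.** The point stands as a weakness in the stated procedure. The documents place the next number and its assignment at the site, in an open-label trial of plainly different products, and describe no step that hides the allocation until enrolment is final. Foreknowledge of pessary versus capsule, and selection bias in the pessary-versus-control comparisons, are not excluded. It is not established that either occurred or would occur.

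The documents do not allow the bias to be sized. The 9% to 15% rejection rates rest on an assumed 60/40 split and assumed risks, and the 44% on an assumed block design; they show only that modest steering could matter with 90 per group. The 6.3 g versus 7.7 g comparison is not shown to be exposed. The sample size is unaffected.

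**What to change.** In Protocol 5.3 and SAP section 3:

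1. Replace assignment by the site coordinator with release by the sponsor employee who already holds the list, by phone, e-mail or web. Release the number and container code only after consent, eligibility and baseline cervical length have been recorded.
2. State that the woman counts as randomised from the moment of release.
3. Use container kit codes that do not follow the randomisation order.
4. If central release is not possible, use sequentially numbered opaque sealed envelopes or identical sealed outer packs.
5. Do not disclose any blocking to the sites.

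The cost is a short amendment, one contact and a short delay per enrolment, and kit relabelling. If an adequate method is already in use, describing it in both documents would be enough.

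If recruitment is over, the report should state the concealment actually used and compare baseline cervical length and prior preterm birth by arm and site. That comparison can reveal steering on recorded factors but cannot exclude it on others.
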